2.1.1 Demographic and baseline characteristics

Demographic characteristics

The following demographic characteristics will be summarized:

Age (years)

Age group (age <18, 18 ≤ age <65, 65 ≤ age <75, 75 ≤ age < 85, age ≥85 years)

Gender (Male, Female)

Region (Asia, Latin America, East Europe, Western Countries) following the classification in the parent study

Territory (North America: Canada and USA; European Union: France, Germany, Hungary, Italy, Poland, Spain and United Kingdom; Rest of World: Argentina, Australia, Brazil, Colombia, Chile, Japan, Mexico, Russia, South Africa, South Korea, Taiwan, Turkey and Ukraine)

Race (Caucasian/White, Black, Asian/Oriental, American Indian or Alaska native, Native Hawaiian or other Pacific Islander, Other)

Ethnicity (Hispanic, Not Hispanic)

Height (cm)

Weight (kg)

Weight group (weight <50, 50 ≤ weight <100, weight ≥100 kg)

BMI (kg/m²)

BMI group (BMI<25, 25≤ BMI <30, BMI≥30 kg/m²)

Alcohol drinking frequency (Never, At least monthly, At least weekly and At least daily) and number of standard alcohol drinks on a typical day when drinking (1 or 2, >2)

The data for demographic characteristics will be obtained from the original baselines of the parent studies.

Medical or surgical history

Medical or surgical history includes all the relevant medical (or surgical) history during the lifetime of the patient. This information will be coded to a "Lower Level Term (LLT)", "Preferred Term (PT)", "High Level Term (HLT)", "High Level Group Term (HLGT)", and associated primary "System Organ Class (SOC)" using the version of Medical Dictionary for Regulatory Activities (MedDRA) currently in effect at Sanofi at the time of database locks.

Comorbidity history will be summarized separately. The following comorbid diseases will be summarized.

Atopic dermatitis history (Yes, Ongoing condition)

Allergic conjunctivitis history (Yes, Ongoing condition)

Allergic rhinitis history (Yes, Ongoing condition)

Allergic conjunctivitis history and/or allergic rhinitis history (Yes, Ongoing condition)

Chronic rhinosinusitis history (Yes, Ongoing condition)

Nasal polyposis history (Yes, Ongoing condition)

Eosinophillic esophagitis history (Yes, Ongoing condition)

Food allergy history (Yes, Ongoing condition)

Hives history (Yes, Ongoing condition)

A patient will be considered to have an atopic medical condition if the patient has any of the following: atopic dermatitis, allergic conjunctivitis or allergic rhinitis, eosinophilic esophagitis, food allergy, hives; or has baseline (parent study) total IgE \geq 100 IU/mL and at least one aeroantigen specific IgE is positive (\geq 0.35 IU/mL) at baseline of parent study.

The data of medical or surgical history will be obtained from the original baselines of the parent studies.

Disease characteristics at baseline

The following baseline disease characteristics will be summarized:

- Prior ICS (medium, high as defined in Appendix C) in combination with allowable controller therapy
- Age of asthma onset
- Time since first diagnosis of asthma (years)

(Year of randomization in parent study – Year of first diagnosis of asthma) + (month of randomization in parent study – month of first diagnosis of asthma)/12

- Smoking history (Never, Former)
 - For former smokers,
 - Time since cessation of smoking for former smokers (months) to be derived as (Year of randomization in parent study – Year of cessation)×12 + (month of randomization in parent study – month of cessation)
 - Smoking quantity (Pack-year)
- Time since last asthma exacerbation (months)

(Year of randomization in parent study – Year of last asthma exacerbation)×12 + (month of randomization in parent study – month of last asthma exacerbation)

- Number of asthma exacerbations experienced 1 year before Visit 1 of the parent study
- Number of asthma exacerbations required hospitalization or urgent medical care 1 year before Visit 1 of the parent study
- $FEV_1(L)$
- ACQ-5 score

The data of baseline disease characteristics will be obtained from the original baselines of the parent studies, unless otherwise specified. Any technical detail related to computation, dates, and imputation for missing dates is described in Section 2.5.

2.1.2 Prior or concomitant medications

• Prior medications are any treatments taken by patient prior to the first IMP administration in the parent study. Prior medications can be discontinued before the first IMP administration in parent study or can be maintained during treatment phase in parent study.

- Concomitant medications in parent study are any treatments received by patient concomitantly to the IMP in the parent studies, from (on/after) the first administration of IMP to the end of post-treatment follow-up period.
- Concomitant medications are any treatments received by patient concomitantly to the IMP in the LTS12551 study, from (on/after) the first administration of IMP to the end of post-treatment follow-up period. A given medication can be classified both as a prior medication and as a concomitant medication.

All medications taken at any time either prior to the first IMP administration or on/after the first IMP dose till the end of follow-up period in the parent study are reported in the case report form and obtained from the parent studies. All medications obtained from the parent studies will be coded using the World Health Organization-Drug Dictionary (WHO-DD) using the version currently in effect at Sanofi at the time of database locks.

All medications taken at any time during the LTS12551 study, from the time of first IMP administration to the end of follow-up period, including inhaled corticosteroid (ICS) in combination with other allowable controller therapies (LABA, LTRA, LAMA, theophylline, etc.), albuterol or levalbuterol reliever medications, and the background oral corticosteroids medication (for patients from the EFC13691 study only) are to be reported in the case report form.

All medications collected during the LTS12551 will be coded using the World Health Organization-Drug Dictionary (WHO-DD) using the version currently in effect at Sanofi at the time of database locks.

2.1.2.1 Salbutamol/albuterol or levosalbutamol/levalbuterol reliever medication

Patients may administer salbutamol/albuterol hydrofluoroalkane pressurized MDI or levosalbutamol/levalbuterol hydrofluoroalkane pressurized MDI as reliever medication as needed during the study. Nebulizer solutions with either albuterol / salbutamol or levalabuterol / levosalbutamol may be used as an alternative delivery method.

Study personnel are to convert salbutamol/albuterol nebulizer and levosalbutamol/levalbuterol nebulizer use as shown by the following table:

Salbutamol/Albuterol Nebulizer Solution -Total Daily Dose (mg)	Number of Puffs*
2.5	4
5.0	8
7.5	12
10	16
*Conversion factor: salbutamol/albuterol nebulizer solution (2.5 mg) corresponds to 4 puffs	

Example of salbutamol/albuterol nebulizer-to-puff conversion: patient received 3 salbutamol/albuterol nebulizer treatments (2.5 mg/treatment) between 7 and 11 AM. Total = 7.5 mg → 12 puffs.

Levosalbutamol/Levalbuterol Nebulizer Solution -Total Daily Dose (mg)	Number of Puffs*
1.25	4
2.5	8
3.75	12
5	16
*Conversion factor: salbutamol/albuterol nebulizer solution (2.5 mg) corresponds to 4 puffs	

Example of levosalbutamol/levalbuterol nebulizer-to-puff conversion: patient received 3 levosalbutamol/levalbuterol nebulizer treatments (1.25 mg/treatment) between 7 and 11 AM. Total = 3.75 mg → 12 puffs.

Any technical details related to computation, dates, imputation for missing dates are described in Section 2.5.

2.1.3 Efficacy endpoints

Efficacy endpoints are secondary endpoints of this study. The following efficacy endpoints will be analyzed:

- Number and Annualized rate of severe exacerbation events during the treatment period
- Forced expiratory volume in one second (FEV1)
- Other spirometry endpoints: Percent Predicted FEV1, Forced Vital Capacity (FVC), Forced Expiratory Flow (FEF) 25-75%
- Asthma control questionnaire 5-question version (ACQ-5) score and responder status
- Asthma quality of life questionnaire (AQLQ) score and responder status
- EuroQoL questionnaire (EQ-5D-3L) score
- Morning and evening peak expiratory flow (PEF)
- Morning evening asthma symptom scores
- Number of inhalations / day of salbutamol / albuterol or levosalbutamol / levalbuterol for symptom relief
- Number of Nocturnal awakenings due to asthma symptoms

- Endpoints linked to the prescribed oral corticosteroids (OCS) dose for the patients from the EFC13691 study:
 - Percentage change from baseline in OCS dose, where the baseline OCS dose is the original baseline from EFC13691
 - Proportion of patients achieving a reduction of 50% or greater in OCS dose compared with the original baseline in the parent study
 - Proportion of patients whose background OCS are completely tapered off

For the above efficacy endpoints, except for the number of severe exacerbations, ACQ-5/AQLQ responder, and the three endpoints particularly for the patients from EFC13691, the change from baseline over time will also be analyzed. The baseline values are the original baselines from the parent study.

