ENDPOINT(S)	
Primary endpoint
 
 • The number (n) and percentage (%) of patients experiencing any treatment-emergent adverse events (TEAEs). 
Secondary endpoints
 
 • Safety and tolerability 
 - Vital signs. - Physical examination. - Electrocardiogram (ECG). - Clinical laboratory tests. • Efficacy 
 - Forced expiratory volume in 1 second (FEV₁). - Asthma Control Questionnaire–5 question version (ACQ-5). - Severe asthma exacerbation events, during the treatment period. - Asthma Quality of Life Questionnaire - Standardized [AQLQ(S)]. - EuroQol 5 dimensions questionnaire, 3-level version (EQ-5D-3L). - Health care resource utilization questionnaire. - Morning and evening peak expiratory flow (PEF). - Asthma symptom scores. - Number of inhalations/day of salbutamol/albuterol or levosalbutamol/levalbuterol for symptom relief.

	
 - Nocturnal awakenings due to asthma requiring use of reliever medication. - Prescribed OCS dose for patients from the EFC13691 study. • Dupilumab systemic exposure and anti-drug antibodies 
 - Serum dupilumab concentrations. - Anti-drug antibodies. • Biomarkers 
 - Blood: Eosinophil count. - Serum: Immunoglobulins (Ig), total IgE.

ASSESSMENT SCHEDULE
	
 • Enrollment period: Combined V1/V2 Visit: Eligible patients from PDY14192, EFC13579, and EFC13691 studies should rollover into LTS12551 on the same day as the end-of-treatment visit of the parent study. • Treatment period: Open-label treatment for 48 weeks (1 year) for patients enrolled after approval of Amendment 04 or 96 weeks (2 years) for patients enrolled prior to Amendment 04 approval. • Post-treatment period: 12 weeks. 
Study visits are performed q2w (ie, twice a month / approximately q2w) during the first 3 months of study (up to Visit 8), every month during the next 3 months (up to Visit 11), and every 3 months up to the End-of-Treatment (EOT) Visit. In addition, monthly telephone contacts will be performed after Week 24/Month 6 (Visit 11).

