9.2.2 Efficacy

The following efficacy **parameters** will be analyzed (see [Section 11.4.2](#) for analysis):

- Forced expiratory volume in 1 second (FEV₁) (see [Section 9.2.2.1](#)).
- Asthma Control Questionnaire – 5 question version (ACQ-5) (see [Section 9.2.2.2](#)).
- Severe asthma exacerbation events during the treatment period (see [Section 9.2.2.3](#)).

- Asthma Quality of Life Questionnaire - standardized [AQLQ(S)] (see [Appendix E](#)).
- EuroQol 5 dimensions questionnaire 3-level version (EQ-5D-3L) (see [Section 9.2.2.5](#)).
- Health care resource utilization questionnaire (see [Section 9.2.2.6](#)).
- Morning and evening peak expiratory flow (PEF) (see [Section 9.2.2.7.1](#)).
- Morning and evening asthma symptom scores (see [Section 9.2.2.7.2](#)).
- Number of inhalations/day of salbutamol/albuterol or levosalbutamol/levalbuterol for symptom relief (see [Section 9.2.2.7.3](#)).
- Nocturnal awakenings due to asthma requiring the use of reliever medication (see [Section 9.2.2.7](#)).
- Prescribed OCS dose for patients from the EFC13691 study (see [Section 9.2.2.8](#)).

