9.2.2.7.1 Record the number of nocturnal awakenings and Peak expiratory flow

Prior to Amendment 04, at Visit 1, patients were issued an electronic PEF meter for recording morning (AM) and evening (PM) PEF, daily salbutamol/albuterol or levosalbutamol/levalbuterol, morning and evening asthma symptom scores, number of nocturnal awakenings due to asthma symptoms and number of night time awakenings due to asthma symptoms that required reliever medications. Patients were instructed on the use of the device, and written instructions on the use of the electronic PEF meter were provided to the patients. In addition, the Investigator instructed the patients on how to record the following variables in the electronic PEF meter:

- AM PEF performed within 15 minutes after arising (between 5:30 AM and 10:00 AM) prior to taking any albuterol or levalbuterol.

- PM PEF performed in the evening (between 5:30 PM and 10:00 PM) prior to taking any albuterol or levalbuterol.
- Patients should try to withhold albuterol or levalbuterol for at least 6 hours prior to measuring their PEF.
- Three PEF efforts will be performed by the patient; all 3 values were recorded by the electronic PEF meter, and the highest value will be used for evaluation.

Baseline AM PEF will be the mean AM measurement recorded for the 7 days prior to the first dose of IMP, and baseline PM PEF will be the mean PM measurement recorded for the 7 days prior to the first dose of investigational product or at least 4 days' measurement for setting up the stability limit, prior to dosing in the LTS12551 study.

9.2.2.7.2 *Asthma Symptom Score*

Prior to Amendment 04, patients recorded overall symptom scores twice a day prior to measuring PEF. The patient's overall asthma symptoms experienced during the waking hours were recorded in the evening (PM symptom score). Symptoms experienced during the night were recorded upon arising (AM symptom score). Baseline symptom scores will be the mean AM and mean PM scores recorded for the 7 days prior to the first dose of investigational product. Patients were instructed to record the severity of symptoms as follows:

AM symptom score:

- 0 = No asthma symptoms, slept through the night;
- 1 = Slept well, but some complaints in the morning. No nighttime awakenings;
- 2 = Woke up once because of asthma (including early awakening);
- 3 = Woke up several times because of asthma (including early awakening);
- 4 = Bad night, awake most of the night because of asthma.

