2.1.3.6 Daily efficacy assessments

On a daily basis before the approval of protocol amendment 4, the patient uses an electronic diary / PEF meter to:

- Measure morning and evening PEF
- Respond to the morning and evening asthma symptom scale questions
- Indicate the number of inhalations / day of salbutamol / albuterol or levosalbutamol / levalbuterol for symptom relief
- Record the number of nocturnal awakenings

The use of the electronic diary/PEF meter will be stopped after the approval of protocol amendment 4. The analyses in LTS12551 study for the above four daily efficacy endpoints in this section will be restricted to the patients from DRI12544 study and performed to the data observed up to the end of collection.

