2.1.3.6.1 Peak expiratory flow

At Visit 1, patients are issued an electronic PEF meter to record morning (AM) and evening (PM) PEF, daily salbutamol/albuterol or levosalbutamol/levalbuterol, morning and evening asthma symptom scores, and number of nighttime awakenings due to asthma symptoms that require reliever medications. Patients are instructed on the use of the device, and written instructions on the use of the electronic PEF meter are provided to the patients. In addition, the investigator instructs the patients on how to record the following variables in the electronic PEF meter:

- AM PEF performed within 15 minutes after arising (between 5:30 AM and 10 AM) prior to taking any salbutamol/albuterol or levosalbutamol/levalbuterol
- PM PEF performed in the evening (between 5:30 PM and 10 PM) prior to taking any salbutamol/albuterol or levosalbutamol/levalbuterol
- Patients should try to withhold salbutamol/albuterol or levosalbutamol/levalbuterol for at least 6 hours prior to measuring their PEF
- Three PEF efforts are performed by the patient; all 3 values will be recorded by the electronic PEF meter, and the highest value will be used for evaluation and it is called PEF maximum (MAX). If more than 3 PEF readings are captured, the highest value of 3 readings closest to the Diary start date and time is the PEF MAX. If only 2 PEF readings are captured, the maximum of the 2 PEF readings captured is the PEF MAX. If only 1 PEF readings is captured, the PEF MAX is treated as missing.

Baseline AM/PM PEF is calculated based on the original baseline values from the parent studies. Baseline AM PEF is the mean AM PEF MAX measurements from the 7 morning diaries

(minimum of 4) prior to randomization in parent study, including the morning diary completed on the randomization day prior to the first dose of IMP. Out of the 7 diaries, if less than 4 have missing PEF value, the baseline AM PEF is the mean of the completed AM PEF MAX within the 7 diaries. If 4 or more diaries have missing AM PEF MAX value, the baseline AM PEF is the mean of the 4 AM PEF MAX prior to and closest to randomization during the whole screening period in parent study.

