2.1.3.6.4 Nocturnal awakenings

The number of nocturnal awakening because of asthma symptoms is recorded every morning by the patients in an electronic diary. The baseline number of nocturnal awakenings is obtained from the original baselines of parent studies, and is computed following the same algorithm used for AM PEF.

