Appendix B Summary of statistical analyses

EFFICACY ANALYSIS

Endpoint	Analysis population	Primary analysis	Statistical Method	Supportive analysis	Subgroup analysis	Other analyses
FEV1, % Predicted FEV1, FVC and FEF 25-75%	Safety	Measurement and change from baseline at all visits	Descriptive statistics	No	Yes (Baseline ICS dose and EOS count subgroups)	No
Severe exacerbation: number of events/annualized event rate during the treatment period	Safety	Summary of number/annualized rate of severe exacerbation events during the treatment period	Descriptive statistics	No	Yes (Baseline ICS dose and EOS count subgroups)	No
Morning asthma symptom score	Safety	Measurement and change from baseline at all visits, for patients from the DRI12544 study only	Descriptive statistics	No	No	No
Evening asthma symptom score	Safety	Measurement and change from baseline at all visits, for patients from the DRI12544 study only	Descriptive statistics	No	No	No
ACQ-5 score	Safety	Measurement, change from baseline, and responder status at all visits	Descriptive statistics	No	Yes (Baseline ICS dose and EOS count subgroups)	No
AQLQ overall score	Safety	Measurement, change from baseline, and responder status at all visits, excluding patients from the PDY14192 study	Descriptive statistics	No	Yes (Baseline ICS dose and EOS count subgroups)	No
AM PEF	Safety	Measurement and change from baseline at all visits, for patients from the DRI12544 study only	Descriptive statistics	No	No	No
PM PEF	Safety	Measurement and change from baseline at all visits, for patients from the DRI12544 study only	Descriptive statistics	No	No	No
Number of inhalations/day of	Safety	Measurement and change from baseline at all visits, for patients from the DRI12544 study only	Descriptive statistics	No	No	No

Statistical Analysis Plan	20-Jul-2017
SAR231893-LTS12551 - dupilumab	Version number: 3

Endpoint	Analysis population	Primary analysis	Statistical Method	Supportive analysis	Subgroup analysis	Other analyses
reliever medication						
Number of nocturnal awakenings	Safety	Measurement and change from baseline at all visits, for patients from the DRI12544 study only	Descriptive statistics	No	No	No
EQ-5D-3L single utility score and VAS	Safety	Measurement and change from baseline at all visits, for patients from the DRI12544 study only	Descriptive statistics	No	No	No

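### The SAP drops the reliever-use condition from the protocol's nocturnal-awakenings endpoint without recording a change, so it most likely tabulates a different diary count

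*SAP*

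**What the plan says.** The protocol names the endpoint twice, each time with a reliever condition. The synopsis has "Nocturnal awakenings due to asthma requiring use of reliever medication" and Section 9.2.2 has "Nocturnal awakenings due to asthma requiring the use of reliever medication". Section 9.2.2.7.1, on what patients entered in the device before Amendment 04, lists two items: "number of nocturnal awakenings due to asthma symptoms and number of night time awakenings due to asthma symptoms that required reliever medications".

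The SAP endpoint list (2.1.3) has "Number of Nocturnal awakenings due to asthma symptoms". The daily-assessment list (2.1.3.6) has "Record the number of nocturnal awakenings". The section devoted to the variable (2.1.3.6.4) reads "The number of nocturnal awakening because of asthma symptoms is recorded every morning by the patients in an electronic diary", and takes the baseline from the parent study by the algorithm used for morning peak flow. The Appendix B row is "Number of nocturnal awakenings", analysed as measurement and change from baseline. The reliever condition appears in the SAP in one place only, the description of the peak-flow meter in 2.1.3.6.1, where the device is said to capture the "number of nighttime awakenings due to asthma symptoms that require reliever medications".

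SAP 2.1.3.6 limits the daily endpoints to patients from DRI12544 and to data observed before diary collection stopped.

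**The concern.** An endpoint that needs reliever use to count an awakening differs from one that counts every asthma awakening. The protocol treats them as two recorded quantities, so the SAP label cannot simply be taken as shorthand for the protocol's endpoint. If the SAP is followed, the clinical study report would probably show the count that the protocol did not name, and the named count would not appear at all.

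Two further things are at stake. First, a programmer working from the SAP alone meets two descriptions of the source field and could pick either. Second, the morning symptom score already grades whether the patient woke once or several times from asthma. An unqualified awakening count therefore overlaps with another reported endpoint, whereas the reliever-requiring count adds separate information.

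**Working it through.** There is no planned figure to reproduce. The check sets every mention of the variable side by side.

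| Place | Role of the text | Reliever condition? |
|---|---|---|
| Protocol synopsis, endpoints | names the endpoint | yes |
| Protocol 9.2.2 | names the endpoint | yes |
| Protocol 9.2.2.7.1, body | lists what was recorded | both counts, separately |
| SAP 2.1.3 | names the endpoint | no |
| SAP 2.1.3.6 | lists daily tasks | no |
| SAP 2.1.3.6.1 | describes the meter | yes, and the only awakening item listed |
| SAP 2.1.3.6.4 | defines the variable and its baseline | no |
| SAP 2.5.2, Table 4 | averaging periods | no |
| SAP Appendix B | summary of analyses | no |

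**Are the two counts the same thing?** No. Let R be the awakenings that needed reliever and N the asthma awakenings that did not. The protocol endpoint is R; the count in SAP 2.1.3.6.4 is A = R + N. Since N ≥ 0, A ≥ R, with equality only if every asthma awakening led to reliever use. The documents give no awakening data, so A − R cannot be estimated.

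**Was the change recorded?** SAP 1.5 lists the statistical changes from protocol Amendment 4; none concerns this definition. SAP 1.6 mentions nocturnal awakenings once, under version 2, to restrict the analysis to DRI12544 patients and to data collected before the diary stopped. Neither section mentions removal of the reliever condition.

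**Which field would a programmer use?** Section 2.1.3.6.1 points to R and Section 2.1.3.6.4 to A. The latter defines the endpoint and agrees with the label in 2.1.3, so A is the likelier choice, but the SAP does not settle it.

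**How many patients?** SAP 1.1 gives 776 enrolled in DRI12544. Entry to this study required completing treatment and follow-up there, then meeting the criteria and consenting (Protocol 7.1 and 7.2). The number affected is therefore at most 776, and the roll-over count is not stated. SAP 1.6 says that these patients have more than one year of diary collection, so the table will have content.

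**Can the protocol endpoint be derived?** On-study values should be available if Protocol 9.2.2.7.1 is accurate. Change from baseline needs R at the DRI12544 baseline as well, and neither document says that DRI12544 recorded it.

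**The case against.** The strongest reply is that this is loose wording and not a change of endpoint. SAP 2.1.3.6.1, describing what patients enter in the device, names only the reliever-requiring count. On that reading, the short labels in 2.1.3.6, Table 4 and Appendix B could be abbreviations for it. The protocol is not tidy either: its list of diary tasks in 9.2.2.7 has no awakenings item, the heading of 9.2.2.7.1 carries no reliever condition, and no subsection defines the variable or its baseline. Section 11.4.2 refers to the SAP for further detail on efficacy analyses.

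Part of this stands. A reader might infer that the SAP has certainly switched endpoints and will report an inflated number as reliever-requiring awakenings. The documents do not support that. The source field is ambiguous within the SAP, the all-awakenings count is only known to be equal or larger, and the SAP's label says openly what it counts. A reader might also infer that the protocol endpoint, with its change from baseline, is simply there to be tabulated. That rests on Protocol 9.2.2.7.1 alone for the on-study data, and on nothing in either document for the parent-study baseline.

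The rest does not stand. Both protocol endpoint lists carry the condition, the SAP's endpoint list and definition both omit it, and detail left to the SAP does not cover an unrecorded change in what is counted.

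It is also fair to say that little depends on this. Efficacy is descriptive with no confirmatory analysis (SAP 2.4.4), diary collection has ended, and awakenings are not among the key efficacy variables chosen for subgroups (SAP 2.4.4.1). That bears on priority, not on whether the discrepancy exists.

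**Conclusion.** The discrepancy is real and minor. The SAP omits the protocol's reliever condition where it names, defines and summarises the endpoint, does not record the change, and contradicts itself on the source variable. As written it most likely reports all asthma awakenings in place of the protocol's count, with a value equal to or larger than the protocol's by an unknown amount.

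The effect is confined to one descriptive secondary endpoint in at most 776 DRI12544 roll-over patients, up to the end of diary collection. The primary endpoint and the study size do not depend on it. The conclusion assumes that Protocol 9.2.2.7.1 correctly describes two separately recorded counts, and that SAP 2.1.3.6.4, as the defining section, governs over the device description in 2.1.3.6.1.

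**What to change.** In SAP 2.1.3, 2.1.3.6.4 and Appendix B, name the reliever-requiring count as the protocol endpoint and show all asthma awakenings as an additional line. Align the short labels in 2.1.3.6 and Table 4. Reconcile 2.1.3.6.1 with 2.1.3.6.4 so that both state which fields the diary holds.

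Before finalising, check whether DRI12544 recorded the reliever-requiring count at its baseline. If it did, derive the baseline from that same variable and report change from it. If it did not, say so and report observed values only. If the reliever-requiring count proves unusable in this study, keep the all-awakenings count but record and justify the substitution in SAP 1.6.

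The cost is a few lines of SAP text and one more diary variable to tabulate, which the protocol says was collected. The drawback is that a parent-study baseline may not exist for it.
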